7.1.3 Analysis Sets

All-Consented (AC): includes all subjects who properly signed the study-specific informed consent (IC). This patient set will be used to summarize patient disposition.

Full Analysis Set (FAS): includes all Primary Cohort subjects, using the intention-to-treat (ITT) principle, who initiate the aDBS Evaluation Phase using the randomized treatment assignment for each subject that was randomized and the programmable treatment assignment for those subjects that may only be configured to one aDBS mode (dual or single threshold).

As-Treated (AT): includes all Primary Cohort subjects who are treated with cDBS and/or aDBS during the cDBS Baseline Evaluation Phase and/or the aDBS Evaluation Phase, and Long-term Follow-up Phase and uses the observed treatment used for each subject in each phase.

All-Randomized (AR): includes all Primary Cohort subjects who were randomized in the aDBS Evaluation Phase, excludes those that were not configured to both modes.

Complete-Case (CC): FAS without imputation that includes all Primary Cohort subjects who have available measures for the respective analysis and are analyzed in their randomization group for those randomized or the programmable treatment for those configured to one aDBS mode.

Directional Stimulation As-Treated (DSAT): includes all Directional Stimulation Cohort subjects who have SenSight leads in a directional stimulation configuration who are treated with continuous Deep Brain Stimulation (cDBS) and/or adaptive Deep Brain Stimulation (aDBS) during the cDBS Baseline Evaluation Phase and/or the aDBS Evaluation Phase, and Long-term Follow-up Phase and uses the observed treatment used for each subject in each phase.

Directional Stimulation Complete-Case (DSCC): includes all Directional Stimulation Cohort subjects who completed the aDBS Evaluation Phase.

7.2 General Methodology

The ADAPT-PD Trial will be considered successful when the primary objective of the study is met for one or both aDBS algorithms independently or the algorithms combined.

The main analysis of the study objectives will use the FAS which includes all Primary Cohort subjects, using the ITT principle, who initiate the aDBS Evaluation Phase using the randomized treatment assignment for each subject that was randomized and the programmable treatment assignment for those subjects that may only be configured to one aDBS mode (dual or single threshold).

The main analysis will include data from all contributing geographies and centers. A poolability analysis for a center effect will be performed as described in Section 7.3.

The subjects' baseline status will be summarized with standard descriptive summary statistics, including counts and percentages for categorical variables, and mean, standard deviation for continuous variables. Safety data will be summarized as specified in Section 7.10.

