13.2.9. Pooling of aDBS mode

Most planned analyses for the Primary Cohort are to be done separately for each mode. Summary statistics will be computed to summarize the percentage who were programmed to each mode and subject characteristics of each subgroup. If fewer than 24 subjects are programmed to one of the aDBS modes because aDBS is unacceptable as compared to cDBS (using the aDBS GIC), the evaluation of aDBS effectiveness will use data from the first period of the aDBS Evaluation Phase from all subjects. If the modes are considered poolable, the modes would be combined and the alpha level of the test would be alpha=0.025 (one-sided). To test for a treatment difference in the first period by aDBS mode group, subjects will be categorized based on the modes they are programmable to: aDBS – Dual Threshold only; aDBS – Single Threshold only; and aDBS – both modes. The Freeman and Halton's extension of Fisher's exact test will be computed testing for differences between aDBS modes in the proportion of subjects exceeding threshold for the primary outcome using data only from the first period. The same categorization of mode will be used and tested using F-tests using linear regression models for the secondary outcome measure. P-values >0.1 for the tests of association with aDBS mode group will be deemed as supporting the assumption of no aDBS mode group effect and the data will be considered poolable across aDBS mode groups. If the aDBS mode group factor approaches statistical significance

(defined as ≤ 0.1),^k the data will not be considered poolable. A minimum of 8 subjects per aDBS mode will be required for the pooled analysis using the first period outcome data.

If data are pooled, missing data observed in the cDBS Baseline Phase and aDBS Evaluation Period 1 will be imputed as described in 13.2.5.

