7.2.1 Pooling of aDBS mode

Most planned analyses for the Primary Cohort are to be done separately for each mode. Summary statistics will be computed to summarize the percentage who were programmed to each mode and subject characteristics of each subgroup. If fewer than 24 subjects are programmed to one of the aDBS modes because aDBS is unacceptable as compared to cDBS (using the aDBS Global Impression of Change [GIC]), the evaluation of aDBS effectiveness will use data from the first period of the aDBS Evaluation Phase from all subjects. If the modes are considered poolable, the modes would be combined and the alpha level of the test would be $\alpha=0.025$ (one-sided). To test for a treatment difference in the first period by aDBS mode group, subjects will be categorized based on the modes they are programmable to: aDBS – Dual Threshold only; aDBS – Single Threshold only; and aDBS – both modes. The Freeman and Halton's extension of Fisher's exact test will be computed testing for differences between aDBS modes in the proportion of subjects exceeding threshold for the primary outcome using data only from the first period.

The same categorization of mode will be used and tested using F-tests from linear regression models for the secondary outcome measure.

[REDACTED]

[REDACTED]

[REDACTED]

P-values >0.1 for the tests of association with aDBS mode group will be deemed as supporting the assumption of no aDBS mode group effect and the data will be considered poolable across aDBS mode groups. If the aDBS mode group factor approaches statistical significance (defined as ≤ 0.1),¹ the data will not be considered poolable. A minimum of 8 subjects per aDBS mode will be required for the pooled analysis using the first period outcome data.

If data are pooled, missing data observed in the cDBS Baseline Phase and aDBS Evaluation Period 1 will be imputed as described in 7.4.

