7.5 Adjustments for Multiple Comparisons

In the Primary Cohort, the familywise error rate will be controlled using one-sided tests with an overall alpha-level of 0.025. Each primary hypothesis (one for each aDBS mode) will be assigned a Bonferroni corrected alpha (0.0125) for the respective primary hypothesis (0.025/2). The primary hypothesis will serve as a gatekeeper for the secondary hypothesis within each mode. No adjustments of multiple comparisons are needed for the Directional Stimulation Cohort as no hypothesis testing will be conducted.

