7.9.1.4 Analysis methods

The primary analysis will use the FAS as described in section 7.1.3. The PD Home Diary will be collected for at least 3 consecutive days (24 hour “periods”) prior to each visit to evaluate the primary objective. Complete diary periods collected anytime during the cDBS Baseline period will be used for analysis as subjects should be on stable cDBS stimulation from enrollment through the end of this period. In the aDBS Evaluation Phase, diary periods will be defined starting with the first completed diary record which is no more than 14 days prior to the visit. If diary is collected more than 14 days prior to the visit, the diary may be used for analysis if there is no change in aDBS stimulation settings. Complete diary periods are defined as any diary period where at least 21 hours (defined as 42 30-minute records) of diary were completed during the 24-hour period, and only complete periods will be used for analysis. If the diary is collected for more than 3 complete periods, up to 7 which are closest to the visit will be used for the analysis, while if a subject has zero complete periods, their diary will be considered missing. Diaries with at least 1 complete period available will be used for analysis. Data from non-contiguous complete periods may be used in the analysis.

The change in daily “On” time without troublesome dyskinesia from cDBS to aDBS will be computed for each subject. The overall standard deviation of the change will be computed for the FAS. The threshold will be set as 1 standard deviation. If the difference between aDBS and cDBS (aDBS-cDBS) for each subject is at least -1 standard deviation, the threshold will be met for the subject. Using this threshold, the proportion of subjects who exceed the threshold will be computed. The proportion with “On” time without troublesome dyskinesia during the respective aDBS Evaluation Period that exceed the threshold will be compared to the performance goal of 50% for each aDBS mode separately using a binomial exact test. The objective will be considered passed if the p-value is less than 0.0125. The lower bound of the 97.5% confidence interval will also be presented.

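### When fewer than 24 subjects have a mode, the plan adds a pooled test at 0.025 without saying that it replaces the two mode tests, and it gives no rule for the not-poolable case

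*SAP*

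**What the plan says.** **Error rate.** SAP 7.5 states that "the familywise error rate will be controlled using one-sided tests with an overall alpha-level of 0.025" and spends all of it on two tests: "Each primary hypothesis (one for each aDBS mode) will be assigned a Bonferroni corrected alpha (0.0125) for the respective primary hypothesis". Protocol 13.2.3 has the same split. Neither section mentions a pooled test.

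**Per-mode pass rule.** SAP 7.9.1.4 says: "The objective will be considered passed if the p-value is less than 0.0125". Protocol 13.4.4 agrees. Neither makes an exception for pooling.

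**Success rule.** SAP 7.2 and protocol 13.1 accept a pass by one mode, by both, or by the combination, as in "met for one or both aDBS algorithms independently or the algorithms combined".

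**Pooled branch.** SAP 7.2.1 and protocol 13.2.9 begin it with "If fewer than 24 subjects are programmed to one of the aDBS modes because aDBS is unacceptable as compared to cDBS". From that point "the evaluation of aDBS effectiveness will use data from the first period of the aDBS Evaluation Phase from all subjects". If the modes are poolable (p > 0.1 across the groups Dual only, Single only and both, with at least 8 subjects per mode), then "the modes would be combined and the alpha level of the test would be alpha=0.025 (one-sided"). If they are not, the text says only that the data will not be considered poolable. It does not say which test follows, on which data or at which alpha. SAP 7.2.1 has blacked-out lines, but the matching protocol section is fully readable and contains no such rule.

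**The concern.** The overall 0.025 is the error guarantee behind the primary claim of a pivotal trial. In the triggered branch, three routes to success can be read from the text: Dual at 0.0125, Single at 0.0125 and pooled at 0.025. The success rule joins them with an or, and the alpha section accounts for two of them. An analyst could claim success by any of the three and cite the plan.

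The second gap is in the same branch. The move to first-period data depends only on the count of subjects per mode and comes before poolability is tested. If the modes then prove different, which is when evidence for each mode matters most, a literal reader would discard second-period data that were collected.

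**Working it through.** **1. The plan's own figures.** 0.0125 + 0.0125 = 0.025, as stated. For n = 36, goal 50%, true proportion 85% and one-sided alpha 0.0125, the exact binomial test passes at 26 or more of 36. Attained alpha is 0.0057 and power 0.986, which agrees with the stated minimum of 90%. 40 × 0.90 = 36 also agrees.

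**2. Nominal error with the third route.**
- Upper bound: 0.0125 + 0.0125 + 0.025 = 0.05.
- If the tests were independent: 1 − 0.9875² × 0.975 = 0.0492.
- Allowing for shared subjects (normal approximation, no poolability pre-test): about 0.037 to 0.043.

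**3. Actual error.** This was simulated with a true proportion of 0.5 in each mode, exact binomial tests, and a pooled pass counted only when the Freeman-Halton p-value exceeds 0.1. The documents give no within-subject correlation between modes, so the ranges below cover assumed values of 0 to 0.6. Layouts are Dual only / both / Single only. The last column uses the pooled test if poolable and all-period mode tests otherwise.

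| Layout | All routes kept, mode tests on all periods | All routes kept, mode tests on period 1 | Pooled test replaces mode tests |
|---|---|---|---|
| N=40: 20/20/0 | 0.026-0.028 | 0.030 | 0.020 |
| N=40: 16/20/4 | 0.029-0.031 | 0.024 | 0.021 |
| N=40: 18/22/0 | 0.028-0.031 | 0.028-0.029 | 0.020 |
| N=40: 24/16/0 | 0.029-0.031 | 0.024 | 0.020-0.021 |
| N=42: 26/8/8 | 0.034-0.036 | 0.026 | 0.026-0.027 |
| N=42: 26/4/12 | 0.032-0.033 | 0.028 | 0.028 |

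The two N=42 rows are the worst splits found for the first and last columns, in a grid of 160 splits (N 36 to 55, smaller mode 8 to 23, correlation 0.3).

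- All routes kept, mode tests on all periods: lowest 0.0185. The worst split reaches 0.0357 at correlation 0. Above 0.025 in 49% of splits.
- All routes kept, mode tests on period 1: above 0.025 in 42%.
- Pooled test replaces mode tests: at or below 0.025 in 95%, with 0.0285 at worst. If the not-poolable tests use period 1 only, at or below 0.025 in 91%.

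**4. Cost of first-period data when not poolable.** Take 23 Single subjects, all randomized to both modes. Period 1 then holds 11 or 12 of them in Single. Exact test at 0.0125, true proportion 85%:

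| n | Passes at | Attained alpha | Power |
|---|---|---|---|
| 23 | 18 | 0.0053 | 0.881 |
| 12 | 11 | 0.0032 | 0.444 |
| 11 | 10 | 0.0059 | 0.492 |

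Power is lower at 12 than at 11 because the test is discrete. With N = 40 the other 17 subjects are Dual only, so Dual has 17 + 11 = 28 or 17 + 12 = 29 subjects in period 1 and power of 0.951 or 0.978.

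**The case against.** A reader might infer that the trial runs at 0.05, or that 0.025 fails in the default design. The documents do not support either. The pooled test arises only after the count trigger, with at least 8 per mode and a poolability p-value above 0.1. GIC acceptability is settled at randomization, before any evaluation diary, so the trigger does not itself inflate error. The 0.05 is a bound; the tests overlap and are discrete.

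Replacement is also the more natural reading of SAP 7.2.1. The section opens with separate analyses as the usual case, then describes an exception with one test at the full alpha. On that reading the success rule simply lists what counts in each branch. This stands as the likely intent. It does not settle the matter, because the success rule and the per-mode pass rule carry no exception and the alpha section leaves the branch out.

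On the second gap, SAP 7.2.1 also ties first-period data to the pooled analysis: the minimum of 8 and the imputation rule both refer to it in that setting. Falling back to each mode's own evaluation period is therefore a fair reading too. A reader might infer that half of the smaller mode's data is always lost. That is true only if all its subjects have both modes; single-mode subjects contribute everything in period 1. The other mode may also still succeed.

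Finally, the two gaps do not add up. The larger error rates belong to mode tests on all periods, whereas the power loss belongs to mode tests on period 1.

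**Conclusion.** The point holds for the triggered branch only. Followed literally, the written rules do not guarantee 0.025 there. Error is about 0.02 to 0.036 depending on the split, above 0.025 in roughly half of the layouts examined. The inflation is small, and where the rate stays at or below 0.025 this is owed to the discreteness of the tests in that split rather than to a rule. The not-poolable case lacks a stated data set and alpha; in the extreme layout the literal reading costs the smaller mode about 39 to 44 percentage points of power (88.1 − 49.2 and 88.1 − 44.4).

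The figures assume a binomial null of 0.5 in each mode and the correlations shown. They do not address the threshold being set from the trial's own standard deviation. The 49% and 42% are shares of the grid, not probabilities that the trial will meet such a split.

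**What to change.** In SAP 7.2, 7.2.1, 7.5 and 7.9.1.4, and in protocol 13.1, 13.2.3, 13.2.9 and 13.4.4, write or cross-refer to:

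> If fewer than 24 subjects have a mode: (i) if poolable with at least 8 per mode, the pooled first-period test at one-sided 0.025 replaces both mode tests, and per-mode results are descriptive; (ii) otherwise no pooled test is done, and each mode is tested at 0.0125 using data from all its evaluation periods, subject to the existing carryover rule.

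The plan should also acknowledge that choosing the route by a pre-test on outcome data leaves a small residual: simulated error is at or below 0.025 in about 95% of splits and about 0.0285 at worst.

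The cost is wording only, with no change to data collection or sample size. The downside is that no single-mode claim can be made in branch (i), which giving the pooled test the full alpha already implies. The text should be settled before the data freeze for the Primary Analysis Report.

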7.2.1 Pooling of aDBS mode

Most planned analyses for the Primary Cohort are to be done separately for each mode. Summary statistics will be computed to summarize the percentage who were programmed to each mode and subject characteristics of each subgroup. If fewer than 24 subjects are programmed to one of the aDBS modes because aDBS is unacceptable as compared to cDBS (using the aDBS Global Impression of Change [GIC]), the evaluation of aDBS effectiveness will use data from the first period of the aDBS Evaluation Phase from all subjects. If the modes are considered poolable, the modes would be combined and the alpha level of the test would be $\alpha=0.025$ (one-sided). To test for a treatment difference in the first period by aDBS mode group, subjects will be categorized based on the modes they are programmable to: aDBS – Dual Threshold only; aDBS – Single Threshold only; and aDBS – both modes. The Freeman and Halton's extension of Fisher's exact test will be computed testing for differences between aDBS modes in the proportion of subjects exceeding threshold for the primary outcome using data only from the first period.

The same categorization of mode will be used and tested using F-tests from linear regression models for the secondary outcome measure.

[REDACTED]

[REDACTED]

[REDACTED]

P-values >0.1 for the tests of association with aDBS mode group will be deemed as supporting the assumption of no aDBS mode group effect and the data will be considered poolable across aDBS mode groups. If the aDBS mode group factor approaches statistical significance (defined as ≤ 0.1),¹ the data will not be considered poolable. A minimum of 8 subjects per aDBS mode will be required for the pooled analysis using the first period outcome data.

If data are pooled, missing data observed in the cDBS Baseline Phase and aDBS Evaluation Period 1 will be imputed as described in 7.4.

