9.9.3. Randomization

Day 0 (no greater than 60 days after aDBS setup complete)

Randomization may occur at the aDBS setup visit, at an unscheduled visit during the aDBS Adjustment Period, or as a standalone visit. All subjects for whom aDBS was set up will complete this visit.

The investigator will assess each aDBS mode that was set up utilizing the aDBS Global Impression of Change (GIC) provided in [Appendix A - aDBS Global Impression of Change Score \(GIC\)](#). Efficacy and side effects are assessed on a scale from 1 to 21. The lower the score the better the efficacy and the less side effects. A score of 8 or less indicates the aDBS mode is acceptable. The investigator will also ensure that the subject is comfortable remaining in the aDBS mode(s) for the duration of the trial.

If only one aDBS mode was set up for a subject, they will not be randomized, but the physician should still complete the aDBS GIC and data collection for the visit.

Data will be collected, including the following:

- Concomitant medications
- GIC value for each aDBS mode that was set up
- Adverse Event and device deficiency assessment

For subjects in whom both aDBS modes are acceptable as compared to cDBS (using the aDBS GIC), unblinded site personnel will obtain the randomization assignment via Remote Data Capture (RDC). The randomization assignment can be obtained upon completion of the aDBS GIC and randomization CRFs.

Randomization will occur to one of two possible treatment sequences if both aDBS modes are acceptable as compared to cDBS (using the aDBS GIC) (dual threshold mode followed by single threshold mode or vice versa) and will be stratified by target site location (STN/GPi). The two sequences will be randomly permuted in blocks of two and four. If an aDBS mode is unacceptable as compared to cDBS (using the aDBS GIC), that subject will be assigned the mode which was acceptable. The randomization schedule will be prepared by Medtronic and it will be maintained at Medtronic. Subjects will continue to be blinded to the aDBS mode during the aDBS Evaluation Phase. If the blind is broken, document the reasons for unblinding in the subject's source documentation and report as a deviation.

Following randomization, the clinician will program one group to the randomized aDBS mode.

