Appendix A - aDBS Global Impression of Change Score (GIC)

This scale is used to help assess for acceptability of an aDBS mode vs. cDBS for an individual subject. A lower number is better in terms of acceptability (ie, greater efficacy with minimal side effects).

- “Acceptable”: A selection appearing in the white (unshaded) boxes means the mode has been deemed “acceptable” and is available for selection for that subject in the aDBS Evaluation Phase. The subject may be programmed with this mode.
- “Unacceptable”: A selection appearing in the grey shading means the mode has been deemed “unacceptable” and is eliminated for selection in the aDBS Evaluation Phase. The subject will not be programmed with that mode.

To decide if a mode is acceptable to a subject, the following table will be used:

		Side effects		
Efficacy	None	Does not significantly interfere with patient's functioning	Significantly interferes with patient's functioning	Side effects experienced outweigh efficacy
Vast improvement	01	02	Fail:10	Fail:11
Decided improvement	03	04	Fail:12	Fail:13
Slight improvement	05	06	Fail:14	Fail:15
Unchanged	07	08	Fail:16	Fail:17
Worse	Fail:18	Fail:19	Fail:20	Fail:21

Medtronic Business Restricted

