7.9.2.4 Sample Size justification

The sample size was estimated using a one-sided test ($\alpha=0.0125$) for one mean (PASS 2011 module Tests for One Mean) to compare the difference in aDBS TEED to cDBS TEED of 22 and a standard deviation of 35, a minimum of 36 subjects achieves at least 90% power.

Based on the registry data and the bench testing, a conservative estimate based on the first quartile of TEED data for initial devices in the registry, TEED is expected to decrease 35 and 22 units for aDBS single threshold mode and aDBS dual threshold mode, respectively. A SD of 36 results in a medium to large effect size of 0.629.

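### The pooling check used when fewer than 24 subjects have one mode groups subjects by programmability, so it is weak against a difference between Dual and Single Threshold

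*SAP*

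**What the plan says.** SAP 7.2 counts the trial as successful when the primary objective is "met for one or both aDBS algorithms independently or the algorithms combined", so a combined result is a named route to success.

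SAP 7.2.1 sets out that route, and Protocol 13.2.9 has the same rule. If fewer than 24 subjects are programmed to one mode because it is unacceptable against cDBS, effectiveness is assessed from period 1 of the Evaluation Phase. If the modes are judged poolable, they are combined and tested at one-sided 0.025. The check is a Freeman-Halton exact test, described as "testing for differences between aDBS modes in the proportion of subjects exceeding threshold for the primary outcome". For that test, however, "subjects will be categorized based on the modes they are programmable to", in three groups: Dual only, Single only, both. TEED uses the same grouping with an F-test. A p-value above 0.1 means poolable. In addition, "A minimum of 8 subjects per aDBS mode will be required for the pooled analysis".

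For subjects with both modes acceptable, Protocol 9.9.3 randomises the order: "The two sequences will be randomly permuted in blocks of two and four". About half of them therefore receive each mode in period 1.

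**The concern.** The stated purpose and the consequence both concern modes, but the factor tested is not mode. Both-mode subjects form one group although about half are on Dual and half on Single in period 1. The randomised contrast between modes is thus averaged inside a group. If nobody is Single-only, the test contains no Single group at all.

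The programmability test is still needed: it asks whether the non-randomised single-mode subjects can be combined with the randomised ones. What is missing is a test by the mode assigned in period 1. Without it, a mode below the 50% goal could be carried by the other in a combined pass. For TEED the plan itself expects the modes to differ: "TEED is expected to decrease 35 and 22 units for aDBS single threshold mode and aDBS dual threshold mode".

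**Working it through.** **The plan's own figures.** For 36 subjects, 85% against 50%, one-sided 0.0125, the exact binomial test rejects at 26 or more successes, with size 0.0057 and power 98.6%. This satisfies the stated minimum of 90%. For TEED, 22/35 = 0.629 and power is 91.8%. The documents give no operating characteristics for the pooling check.

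**Inputs from the documents.** 40 subjects entering the Evaluation Phase; poolable if p > 0.1; pooled one-sided alpha 0.025; 85% planned success rate; TEED changes of -35 (Single) and -22 (Dual), SD 35.

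**Assumptions.** The split of subjects is not given, so two layouts (Dual-only/Single-only/both) are used, and outcome is taken to depend only on the mode received.
- 17/8/15, with 8 Dual-first and 7 Single-first. Having fewer than 24 with Single means at most 23; with at least 8 Single-only, at most 23 - 8 = 15 have both. This is the largest both-mode group that keeps 8 in every group.
- 20/0/20, with 10 and 10. This is admissible only if the minimum of 8 is counted by mode received rather than by group.

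**What the written test sees at 85% Dual and 45% Single.** The both-mode rate in 17/8/15 is (8 × 0.85 + 7 × 0.45)/15 = 66%. In 20/0/20 it is (0.85 + 0.45)/2 = 65%, so a 40-point difference between modes appears as 20 points between groups. The expected pooled proportion is (25 × 0.85 + 15 × 0.45)/40 = 70% in 17/8/15 and (30 × 0.85 + 10 × 0.45)/40 = 75% in 20/0/20. The pooled test passes at 27/40 = 67.5%.

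**Primary endpoint.** Exact enumeration of all binomial outcomes, with two-sided p by table probability. Each cell gives the written test, then the written test plus Fisher's test by assigned mode.

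| Dual / Single | Result | 17/8/15 | 20/0/20 |
|---|---|---|---|
| 85 / 45 | poolable | 42% / 14% | 70% / 24% |
| 85 / 45 | poolable and pooled test passes | 32% / 11% | 64% / 21% |
| 85 / 50 | poolable and pooled test passes | 42% / 19% | 72% / 30% |
| 85 / 65 | poolable | 75% / 55% | 89% / 61% |
| 85 / 85 | poolable | 91.6% / 88.4% | 96.5% / 91.7% |

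With 7 Dual-first and 8 Single-first in 17/8/15, the 85/45 joint figures are 28% and 10%.

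**Is the gain only from applying two tests?** No. With each grouping used alone at 85/50, the written grouping detects the difference in 23% to 56% of trials over six layouts that keep at least 8 subjects per mode in period 1; grouping by mode received detects it in 64% to 70%. The written test is not the stricter one: its size is 5% to 9%, against 5% to 6%.

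**Threshold estimated from the data.** SAP 7.9.1.4 says "The overall standard deviation of the change will be computed for the FAS". In 60,000 simulated trials with normal changes, Single shifted by -1.3 within-mode SDs and the SD taken from all 40 period-1 changes, the realised rates in 17/8/15 are 88% and 45%. The joint probability is 28% as written and 7% with both tests.

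**Effect on trial success at 85/45.** Dual alone at 0.0125 passes in 93% (25 subjects, at least 19 successes) and 97% (30 subjects, at least 22). A pooled pass while Dual alone fails occurs in 0.9% and 0.5%. This assumes per-mode testing when the modes are not pooled, which SAP 7.2.1 does not state.

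**TEED, 17/8/15, planning figures.** The both-mode mean is (8 × -22 + 7 × -35)/15 = -28.1, between the other two groups. In 200,000 simulated trials the written F-test flags the difference in 18% and a test by assigned mode in 30%. The modes are declared poolable in 82% as written and 64% with both tests. The pooled mean is (25 × -22 + 15 × -35)/40 = -26.9. With both modes at -22, poolability falls from 90% to 83%.

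**The case against.** - **The effect on the trial's conclusion is small.** This is a fallback branch, familywise error is not inflated, and the better mode usually passes alone. This stands, and it limits the harm to what a combined result can be said to show.
- **45% is extreme.** It needs a mean loss of about 1.3 SDs after a screen in which a mode rated unacceptable "is eliminated for selection in the aDBS Evaluation Phase". This stands too. The gap remains at 85/65, but it narrows: at 85/75 in 17/8/15 the assigned-mode test alone flags 16% against 15% for the written test.
- **Another p > 0.1 gate does not show equality.** True. On the planning TEED figures both tests together still pool in 64% of trials, which is why per-mode results must accompany any pooled one.
- **Per-mode summaries exist elsewhere.** SAP 7.9.3.7 summarises diary On time without troublesome dyskinesia, and SAP 7.9.3 evaluates it separately by mode, so a poor mode would not be invisible. Those summaries do not enter the pooling rule, and no per-mode period-1 proportion is promised beside a pooled result.
- **Part of SAP 7.2.1 is redacted.** The hidden text may hold code. Protocol 13.2.9 is unredacted, prints the same three categories and contains no test by assigned mode, so the hidden text cannot be assumed to change the factor.

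**Conclusion.** The concern holds. The test does not test what the plan says it tests, and it is weak against a mode difference whenever some subjects have both modes. At 85/45 it lets through a combined pass about three times as often as the two tests together (32% against 11%, and 64% against 21%). At 85/65 the excess in pooling is 20 to 28 percentage points. For TEED, the plan's own expected difference is called poolable in 82% of trials.

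These sizes rest on the assumed layouts and rates, and on outcome depending only on mode received. The issue arises only in the under-24 branch and vanishes when nobody has both modes. It should be corrected because a combined result is a named route to success, although it seldom decides whether the trial succeeds.

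**What to change.** In SAP 7.2.1 and Protocol 13.2.9:

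- Keep the programmability-group test and name it as such.
- Add, for each endpoint, a test by the mode assigned in period 1. For the primary endpoint, use Fisher's exact test of Dual against Single. For TEED, use a separate linear model with assigned mode as the only factor; added to the programmability model, mode would be identified only within the both-mode group.
- Pool an endpoint only if both of its own tests give p > 0.1, and state that a TEED result does not block pooling of the primary endpoint. If nobody has both modes, one test is enough.
- As a supporting result, show the mode comparison in randomised both-mode subjects only.
- Beside any pooled result, report each mode's period-1 proportion with its confidence bound.

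The cost is a few sentences and one more test per endpoint on data already collected. When the modes are truly equal, pooling is accepted somewhat less often: 3.2 percentage points less in 17/8/15 and 4.8 in 20/0/20 for the primary endpoint, and about 7 for TEED in 17/8/15.
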